3.3. Inclusion of Minorities and Other Underrepresented Populations

Both men and women are eligible for this protocol. Every effort will be made to include patients from minority populations. Because breast cancer predominantly affects females, it is anticipated that male enrollment will be $< 5\%$ of the overall study population.

4. REGISTRATION PROCEDURES

4.1. General Guidelines for DF/HCC and DF/PCC Institutions

Institutions will register eligible participants with the DF/HCC Quality Assurance Office for Clinical Trials (QACT) central registration system. Registration must occur prior to the initiation of therapy. Any participant not registered to the protocol before treatment begins will be considered ineligible and registration will be denied.

A member of the study team will confirm eligibility criteria and complete the protocol-specific eligibility checklist.

Following registration, participants may begin protocol treatment. Issues that would cause treatment delays should be discussed with the Overall Principal Investigator(PI). If a participant does not receive protocol therapy following registration, the participant's registration on the study may be cancelled. Notify the QACT Registrar of registration cancellation as soon as possible.

4.2. Registration Process for DF/HCC and DF/PCC Institutions

The QACT registration staff is accessible on Monday through Friday, from 8:00 AM to 5:00 PM Eastern Standard Time.

The registration procedures are as follows:

1. Obtain written informed consent from the participant prior to the performance of any study related procedures or assessments.
2. Complete the QACT protocol-specific eligibility checklist using the eligibility assessment documented in the participant's medical record and/or research chart. **To be eligible for registration to the protocol, the participant must meet all inclusion and exclusion criterion as described in the protocol, and reflected on the eligibility checklist.**

Reminder: Confirm eligibility for ancillary studies at the same time as eligibility for the treatment study. Registration to both treatment and ancillary studies will not be completed if eligibility requirements are not met for all studies.

3. Fax the eligibility checklist(s) and all pages of the consent form(s) to the QACT at [contact].
4. The QACT Registrar will (a) review the eligibility checklist, (b) register the participant on the protocol, and (c) randomize the participant when applicable.
5. An email confirmation of the registration and/or randomization will be sent to the Overall PI, study coordinator(s) from the lead site, treating investigator

and registering person immediately following the registration and/or randomization.

4.3. Registration Process for Other Investigative Sites

To register a participant, the appropriate documents should be completed by the research nurse or data manager and faxed [*[contact]*] or e-mailed [*[contact]*] to the Study Project Managers.

Please refer to Appendix 9: Section 3.7.1 for a complete list of appropriate documents.

The research nurse or data manager at the participating site will then e-mail [*[contact]*] the Project Manager to verify eligibility. To complete the registration process, the Project Manager will

- register the participant on the protocol with the QACT
- fax or e-mail the participant study number, and if applicable the dose treatment level to the participating site
- call the research nurse or data manager at the participating site and verbally confirm registration

NOTE: Registration and randomization with the QACT can only be conducted during the business hours of 8:00 AM and 5:00 PM Eastern Standard Time Monday through Friday. Same day treatment registrations will only be accepted with prior notice and discussion with the DF/HCC Lead Institution.

5. TREATMENT PLAN

Treatment will be administered on an outpatient basis. Expected toxicities and potential risks as well as dose modifications for eribulin are described in Section 6 (Expected Toxicities and Dosing Delays/Dose Modification). No investigational or commercial agents or therapies other than those described below may be administered with the intent to treat the participant's malignancy.

5.1. Overall Study Design and Plan

This is a non-randomized, open label study of eribulin monotherapy in the first or second line setting for metastatic HER2-negative breast cancer. Each subject will be assigned a unique identification number during screening, which will be used on all CRFs and correspondence regarding the subject.

Patients receiving monotherapy will be enrolled in 2 parallel cohorts:

- Cohort 1: HR+/HER2-negative (n = 45 pts)

Protocol #:13-077
Version Date: 2/23/2016

- Cohort 2: TNBC (n= 45 pts)

Treatment Description					
Agent	Pre-medications	Dose	Route	Schedule	Cycle Length
Eribulin	none	1.4 mg/m ²	IV over 2 to 5 minutes	Days 1, 8	21 days (3 weeks)

The starting dosage of eribulin mesylate in this study, 1.4 mg/m² administered as an i.v. infusion over approximately 2 to 5 minutes on Days 1 and 8 of a 3-week cycle, is based on results of four Phase 1 and four Phase 2 clinical studies. Four Phase 1 dose-finding studies were conducted to evaluate escalating doses of eribulin mesylate and determine the maximum tolerated dose (MTD) of eribulin mesylate as: (1) a 1-hour i.v. infusion on Days 1, 8 and 15 of a 28-day cycle (E7389-A001-101); (2) a 1-hour i.v. infusion on Day 1 of a 21-day cycle (E7389-A001-102); (3) an i.v. bolus on Days 1, 8 and 15 of a 28-day cycle (National Cancer Institute [NCI] Study 5730); and (4) a bolus infusion on Days 1 and 8 of a 21-day cycle (E7389-J081-105). The MTD was determined to be 1.4 mg/m² for the bolus injection and 1.0 to 2.0 mg/m² for the infusion.

Eribulin mesylate 1.4 mg/m² i.v. bolus was tested as the starting dose in four Phase 2 studies. In the first two Phase 2 studies, subjects initially received eribulin mesylate on Days 1, 8 and 15 in 28-day cycles. Because the majority of subjects receiving the 28-day dosing schedule experienced dose delays, reductions, or omissions due to neutropenia on Day 15 of the cycle, an additional cohort of subjects who received eribulin mesylate 1.4mg/m² on Days 1 and 8 in 21-day cycles was added. This schedule appeared to be better tolerated than the 28-day schedule and demonstrated antitumor activity in all four Phase 2 studies. Thus, the optimal schedule of eribulin mesylate based on the four studies appears to be 1.4 mg/m² administered on Days 1 and 8 in 21-day (3-week) cycles.

5.2. Pretreatment Criteria

Pretreatment criteria will be assessed within 21 days of the first dose of study treatment to establish eligibility and baseline values.

Informed consent will be obtained after the study has been fully explained to the subject and before the conduct of any screening procedures or assessments. If screening assessments occur within 3 days before start of study treatment, then they may serve as the baseline Cycle 1 Day 1 visit and screening tests do not need to be repeated.

Demographic information and baseline characteristics will be collected at the Screening Visit. Standard demographic parameters include age, sex, and race/ethnicity (recorded in accordance with prevailing regulations). Baseline characteristics will include ECOG PS (Appendix 2), NYHA cardiac disease classification (Appendix 4), disease status, medical histories, prior and concomitant medications, and PE findings. Relevant hormone receptor status will be collected.

Within the 21 days prior to therapy initiation patients will undergo baseline clinical evaluation (including history, physical evaluation, vital signs, and performance status). Subsequent changes from screening PE findings that meet the definition of an AE will be recorded on the AE page of the eCRF.

Additional pre-treatment evaluations include: CBC with differential, chemistries, pregnancy test (if indicated), tumor measurements by staging studies and concomitant medication assessment. If eligible and registered, blood collection for correlative studies will occur at Cycle 1 Day 1.

5.3. Treatment Phase

Treatment cycles will begin with the first dose of administration of study treatment on Cycle 1, Day 1 and continue in 3-week (21-day) cycles. Subjects will continue to receive study treatment until the development of Progressive Disease (PD) or the subject meets another withdrawal criterion as described in Section 15. All subjects will receive eribulin mesylate 1.4 mg/m² on Day 1 and Day 8 of each cycle. Subjects will undergo tumor response assessments every 9 weeks.

After PD is documented or if subject is withdrawn from study, study treatment must be discontinued; all enrolled subjects will then be treated according to prevailing local standards at the investigator's discretion. Subjects who discontinue study therapy without PD will continue to undergo tumor response assessments every 9 weeks (from the date of the last tumor assessment) until PD is documented. All subjects will undergo an End-of-Treatment visit within 21 days after the final dose of study treatment.

5.4. Agent Administration

Eribulin Mesylate

Eribulin mesylate 1.4 mg/m² will be administered on an outpatient basis via i.v. infusion over approximately 2 to 5 minutes on Days 1 and 8 of each 3-week cycle. Therapy will continue until PD is documented or another withdrawal criterion is met as specified in Section 5.9. All subjects will receive the same starting dosage of eribulin mesylate, based on BSA.

Please note that minor variations in treatment dates (+/-3 days) may occur depending on physician and patient scheduling, observed holidays, inclement weather, etc. Regardless of the time of administration, toxicity from previous treatment must be within acceptable ranges as described below:

Criteria for Eribulin administration

- Absolute Neutrophil Count $\geq 1,000/\text{mm}^3$ or $\geq 1.0 \times 10^9/\text{L}$
- Platelet Count $\geq 75,000/\text{mm}^3$ or $\geq 75 \times 10^9/\text{L}$
- Non-hematologic toxicity CTCAE \leq Grade 3 or 4

Before dose administration, the amount of eribulin mesylate needed for each subject must be calculated in the following manner:

1. Scheduled dose (mg/m²) x body surface area (m²) = Dose (mg)
2. Dose (mg) x 2 = the number of mL of eribulin mesylate to withdraw from vials for administration

Body surface area (BSA) will be calculated using any method that is accepted and customarily used by the investigational site, such as the Mosteller formula:

$$\text{BSA (m}^2\text{)} = ([\text{Height ([cm]} \times \text{Weight (kg)})] \div 3600)^{1/2}$$

Height and body weight will be recorded at the screening visit. Thereafter, body weight will be recorded on each treatment day and dosing BSA will be calculated accordingly.

The amount of eribulin mesylate required (as calculated above) will be withdrawn from the appropriate number of vials into a syringe. This may be injected directly as an i.v. infusion over approximately 2 to 5 minutes or diluted in up to 100 mL 0.9% saline for i.v. infusion over approximately 2 to 5 minutes. No special tubing is required for the i.v. administration of eribulin mesylate.

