6.2. Eribulin - Toxicity Management

Subjects should be carefully monitored for toxicity. If Grade 3 or 4 toxicities are present, then treatment should be delayed to allow for recovery (see instructions for dose delay below). If toxicities recur, the dose of eribulin should be reduced. In the setting of neutropenia, growth factor support may be added instead of a dose reduction at time of first occurrence of neutropenia at the discretion of the investigator. Once the dose of eribulin is reduced, it may not be increased at a later date. Dose adjustment recommendations for eribulin are shown in Table 1.

Eribulin Dose Levels

Starting dose	1.4 mg/m²
1 st dose reduction	1.1 mg/m ²
2 nd dose reduction	0.7 mg/m ²

Table 1: Dose adjustment recommendations for eribulin

Adverse reaction/Toxicity^a	Grade/Details	Eribulin dose modification
ANC	< 500 cells/mm ³ lasting > 7 days in the previous cycle without use of growth factors	Hold eribulin until recovery to grade ≤ 2. Eribulin may be resumed at the same dose with growth factor support, or it may be reduced by one dose level, per investigator discretion.
	< 500 cells/mm ³ lasting > 7 days in the previous cycle despite use of growth factors	Hold eribulin until recovery to grade ≤ 2, and reduce by 1 dose level.
	<1000 /mm ³ with fever or infection without use of growth factors	Hold eribulin until recovery to grade ≤ 2. Eribulin may be resumed at the same dose with growth factor support, or it may be reduced by one dose level, per investigator discretion.
	<1000 /mm ³ with fever or infection despite use of growth factors	Hold eribulin until recovery to grade ≤ 2, and reduce by 1 dose level.
	<1000 /mm ³ without fever or infection without use of growth factors	Hold eribulin until recovery to grade ≤ 2 then resume at the same dose with growth factor support. If uncomplicated neutropenia lasting < 1 week (<1000 /mm ³ without fever or infection) occurs/recurs despite growth factor support, then hold eribulin until recovery to grade ≤ 2 . Eribulin may be then be resumed at the same dose with growth factor support, or it may be reduced by one dose level, per investigator discretion.

		If uncomplicated neutropenia lasting > 1 week (<1000 /mm ³ without fever or infection) occurs/recurs despite growth factor support, then hold eribulin until recovery to grade ≤ 2 and reduce by 1 dose level.
Platelets	Grade 2	Hold eribulin until recovery to grade 1

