	Grade 3	Hold eribulin until recovery to grade 1 then reduce by 1 dose level.
	Grade 4	Hold eribulin until recovery to grade 1 then reduce by 1 dose level.
Anemia	Grade 4	Hold eribulin until recovery to grade ≤ 2 then reduce by 1 dose level. PRBC transfusions are permitted to treat anemia.
Peripheral neuropathy	Grade 2	For intolerable (as determined by physician and patient) grade 2, decrease chemotherapy by one dose level.
	Grade 3	Hold eribulin until recovery to grade ≤ 2 then reduce by 1 dose level.
	Grade 4	Treatment discontinuation.
Non-hematologic toxicity	Grade 3, first occurrence	Hold eribulin until recovery to grade ≤ 2. Maximize supportive care measures. If symptom recovery occurs within 1 week, then eribulin may be resumed at the same dose if deemed appropriate by the investigator, otherwise, reduce by 1 dose level.
	Recurrent grade 3, or any grade 4 toxicity	Hold eribulin until recovery to grade ≤ 2 then reduce by 1 dose level.
Recurrence of any Grade 3 or 4 event despite reduction to 0.7 mg/m ² , or persistent grade 3 or 4 toxicity lasting more than 3 weeks despite maximal supportive measures		Treatment discontinuation

ANC = absolute neutrophil count a: Toxicities graded in accordance with National Cancer Institute Common Toxicity Criteria for Adverse Events, version 4.0, Appendix 5
		

Instructions for Dose Delay

Criteria to continue treatment

- Absolute Neutrophil Count $\geq 1000/\text{mm}^3$ or $\geq 1.0 \times 10^9/\text{L}$
- Platelet Count $\geq 75,000/\text{mm}^3$ or $\geq 75 \times 10^9/\text{L}$
- Non-hematologic toxicity \leq grade 2

Eribulin will NOT be administered if any of the following values are present on Day 1 or 8 prior to treatment administration:

- Absolute Neutrophil Count $< 1,000/\text{mm}^3$ or $< 1.0 \times 10^9/\text{L}$
- Platelet Count $< 75,000/\text{mm}^3$ or $< 75 \times 10^9/\text{L}$
- Non-hematologic toxicity CTCAE Grade 3 or 4

If the dose of eribulin cannot be administered as planned due to treatment-related toxicity, the dose should be delayed according to the following instructions:

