Day 1 of each cycle: If eribulin cannot be administered on Day 1, the dose should be delayed until recovery to above mentioned values (criteria for eribulin administration). The Day 1 dose will be rescheduled for when the criteria for eribulin administration are being met. The dose of eribulin may have to be reduced following a dose delay in accordance to the instructions for dose reduction (Table 1). A maximum of 3 weeks are allowed for a delay in therapy. If the patient fails to meet the criteria to continue treatment within 3 weeks, they will be removed from the protocol.

Day 8 of each cycle: If eribulin cannot be administered on Day 8, the dose should be delayed until recovery to above mentioned values (criteria for eribulin administration). The Day 8 dose will be **delayed for a maximum of 7 days** and as follows:

- If the criteria for eribulin administration are met on, or before Day 15 of a cycle, administer eribulin as recommended in Table 1; this dose is still called Day 8.
- Eribulin administration on Day 1 of the next cycle should be no sooner than 14 days later.
- If the criteria for eribulin administration are NOT being met by Day 15 of a cycle, omit the Day 8 dose of eribulin for that cycle. Eribulin should be administered as recommended in Table 1 on Day 1 of the next scheduled cycle assuming criteria to continue treatment are met within a maximum 3 week delay in therapy from originally planned day 8.

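### Section 5.4 lets eribulin be given at non-hematologic toxicity up to Grade 3 or 4, where Section 6.2 forbids dosing and requires Grade 2 or lower

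*Combined protocol and SAP*

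**What the plan says.** Section 5.4 (Agent Administration) makes its list a condition of dosing: "toxicity from previous treatment must be within acceptable ranges as described below". The list has three items: neutrophils of at least 1,000/mm³, platelets of at least 75,000/mm³, and "Non-hematologic toxicity CTCAE \leq Grade 3 or 4".

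Section 6.2 (Eribulin - Toxicity Management) covers the same decision four times:

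- Opening text: "If Grade 3 or 4 toxicities are present, then treatment should be delayed to allow for recovery".
- Table 1, non-hematologic toxicity, first Grade 3 event: "Hold eribulin until recovery to grade ≤ 2. Maximize supportive care measures". The next row applies the same hold, followed by a dose reduction, to recurrent Grade 3 and any Grade 4.
- Criteria to continue treatment: "Non-hematologic toxicity \leq grade 2".
- The list introduced by "Eribulin will NOT be administered if any of the following values are present on Day 1 or 8 prior to treatment administration", whose third item is non-hematologic toxicity of Grade 3 or 4.

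Table 1 also stops treatment permanently for Grade 4 peripheral neuropathy.

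The Nursing Protocol Education Sheet, in its row on study drug administration, refers staff to Section 5.4 alone for the criteria to treat. Its separate row on dose modifications and toxicity cites Section 6.2 and Table 1. The introduction to Section 5 also points to Section 6 for toxicities and dose modifications.

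**The concern.** The two sections give different answers to one question: may this patient be dosed today? A patient with a Grade 3 non-hematologic toxicity on Day 1 or Day 8 satisfies the Section 5.4 item but must be held under Section 6.2. If 4 is the ceiling in Section 5.4, the same is true at Grade 4. The error runs in the unsafe direction, towards giving a cytotoxic drug to someone with severe or life-threatening toxicity.

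Section 6.2 comes into play once someone has recognised that the patient should not be dosed. Staff who check only the Section 5.4 list, as the nursing sheet's criteria-to-treat line directs, would pass a Grade 3 patient and have no prompt to consult the delay rules. The protocol does not say which section prevails.

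The threshold itself is not in dispute. Grade 2 or lower is the protocol's own choice in Section 6.2.

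**Working it through.** No sample size, power or error rate is involved, so the check is a comparison of the texts.

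**Step 1. Compare the three items.**

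| Item | Section 5.4: dose if | Section 6.2: continue if | Section 6.2: do not dose if | Agree? |
|---|---|---|---|---|
| Neutrophils | ≥ 1,000/mm³ | ≥ 1,000/mm³ | < 1,000/mm³ | Yes |
| Platelets | ≥ 75,000/mm³ | ≥ 75,000/mm³ | < 75,000/mm³ | Yes |
| Non-hematologic toxicity | ≤ Grade 3 or 4 | ≤ Grade 2 | Grade 3 or 4 | No |

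One item of three conflicts. For the two blood counts, the sign is correctly reversed between the do-not-dose list and the dosing criteria. The third item keeps the barred grades from the do-not-dose list and puts a less-than-or-equal sign in front of them. That pattern suggests a drafting slip.

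**Step 2. Test each reading of the Section 5.4 item.** The phrase names two ceilings, and a program read the sign from a PDF, so a strict less-than sign is tested too. Section 6.2 permits dosing at Grade 2 or lower.

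| Reading of Section 5.4 | Grades at which dosing is allowed | Conflict with Section 6.2 |
|---|---|---|
| ≤ 3 (sign as printed) | up to 3 | Grade 3 |
| ≤ 4 (sign as printed) | up to 4 | Grades 3 and 4 |
| < 3 (if the sign was misread) | up to 2 | none |
| < 4 (if the sign was misread) | up to 3 | Grade 3 |

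As printed, both readings conflict. With the other sign, one of two readings agrees with Section 6.2, and the line would still name two ceilings.

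**Step 3. Check whether the delay rules settle it.** The Day 1 and Day 8 rules in Section 6.2 tell staff that "the dose should be delayed until recovery to above mentioned values (criteria for eribulin administration") must be reached. They use that label five times, and it matches the heading of the Section 5.4 list. They use a second label twice, for example "If the patient fails to meet the criteria to continue treatment within 3 weeks", and that one matches the Section 6.2 heading. The words about values mentioned above most naturally point to the Section 6.2 lists directly preceding them, so the intent can be recovered. The shared label still leaves a route back to Section 5.4.

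**Step 4. Look for a frequency.** The conflict matters only when Grade 3 or 4 non-hematologic toxicity is present on a dosing day. Sections 2.1 and 6.1 report Phase 3 rates of Grade 3 or 4 related events: asthenia/fatigue 7.6%, peripheral neuropathy 8.4%. These are incidences over the whole trial in heavily pretreated patients. They do not give the proportion of dosing visits affected here, so no count is offered.

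**The case against.** The strongest reply is that nobody following the whole protocol would be led astray. Section 5.4 states a necessary condition and does not order dosing whenever its list is met. Section 6.2 is an express prohibition tied to dosing days. Both can be obeyed by following the stricter one, and the introduction to Section 5 sends readers to Section 6. A ceiling of Grade 4 would exclude no living patient, so staff would probably recognise a typing error. The nursing sheet also cites Section 6.2, tells staff to page the research nurse or site investigator with questions, and is headed as one institution's document. Finally, the finding turns on one symbol: if the source has a strict less-than sign, the natural meaning is below the Grade 3 to 4 band, which is Section 6.2's rule.

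Much of this stands. The intended rule is clear once Section 6.2 is read, harm is possible rather than shown, nothing establishes that other sites use the sheet, and a misread sign cannot be excluded. It does not remove the conflict. The other inequality signs in the same list, and the matching sign in Section 6.2, read sensibly. The ceiling-of-3 reading is not absurd on its face and still permits dosing at Grade 3. A go/no-go list for a cytotoxic drug should also be right on its own, without relying on staff to find the correction elsewhere.

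**Conclusion.** The concern holds. As printed, the non-hematologic item in Section 5.4 contradicts four statements in Section 6.2: at Grade 3 on either reading of its ceiling, and at Grade 4 as well if the ceiling is 4. This rests on the sign being as printed. With a strict less-than sign the conflict would disappear only if 3 is the ceiling, and the line would remain ambiguous.

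It must be fixed because it is an operative dosing rule that errs against the patient. That judgement does not depend on how often the situation arises, which the documents cannot show. There is no effect on the sample size or the primary response-rate analysis.

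**What to change.** Replace the third item of the Section 5.4 list with non-hematologic toxicity of CTCAE Grade 2 or lower, which is the limit Section 6.2 already sets. Have the nursing sheet's criteria-to-treat line cite Section 6.2 alongside Section 5.4.

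Two editorial changes can go in the same amendment, though the finding does not depend on them. Use one label for the criteria throughout the Day 1 and Day 8 delay rules. Add an adverse event entry for Day 8 in Section 5.5.2 and Table 3, since Sections 8.1 and 11 already call for assessment at every encounter.

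The cost is a few lines of text by amendment and a memo to sites. No new procedure is needed, and neither the sample size nor the analysis changes.
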